13.3 Stratification Factors

n/a

13.4 Analysis of Secondary Endpoints

Responses will be determined using RECIST as described in Section12 and summarized in tabular format. The complete and partial response rates will be calculated and reported along with the corresponding 95% confidence intervals. All eligible subjects (intent-to-treat population) will be included in the calculation of the response rate. Progression-free survival will be analyzed using the Kaplan-Meier method.

PK parameters (based on ideal body weight and actual body weight) of the study participants will be summarized using standard descriptive statistics in terms means, standard deviations and ranges. A two-sample t-test will be used to compare the mean values in the PK parameters in obese patients with normal weight historical controls.

13.5 **Reporting and Exclusions**

13.5.1 **Evaluation of toxicity.** All patients will be evaluable for toxicity from the time of their first treatment with capecitabine.

13.5.2 **Evaluation of response.** All patients included in the study must be assessed for response to treatment, even if there are major protocol treatment deviations or if they are ineligible. Each patient will be assigned one of the following categories: 1) complete response, 2) partial response, 3) stable disease, 4) progressive disease, 5) early death from malignant disease, 6) early death from toxicity, 7) early death because of other cause, or 9) unknown (not assessable due to measurable disease only or insufficient data). [Note: By arbitrary convention, category 9 usually designates the "unknown" status of any type of data in a clinical database.]

All of the patients who met the eligibility criteria (with the possible exception of those who received no study medication) should be included in the main analysis of the response rate. Patients in response categories 4-9 should be considered to have a treatment failure (disease progression). Thus, an incorrect treatment schedule or drug administration does not result in exclusion from the analysis of the response rate.

All conclusions should be based on all eligible patients. Subanalyses may then be performed on the basis of a subset of patients, excluding those for whom major protocol deviations have been identified (e.g., early death due to other reasons, early discontinuation of treatment, major protocol violations, etc.). However, these subanalyses may not serve as the basis for drawing conclusions concerning treatment efficacy, and the reasons for excluding patients from the analysis should be clearly reported. The 95% confidence intervals should also be provided.

REFERENCES:

1. Griggs JJ, Mangu PB, Anderson H, et al. Appropriate chemotherapy dosing for obese adult patients with cancer: American Society of Clinical Oncology clinical practice guideline. J Clin Oncol;30:1553-61.

2. (Accessed June 21, 2012, at http://www.cdc.gov/obesity/data/adult.html.)

3. Mosteller RD. Simplified calculation of body-surface area. The New England journal of medicine 1987;317:1098.

4. Pinkel D. The use of body surface area as a criterion of drug dosage in cancer chemotherapy. Cancer Res 1958;18:853-6.

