3. PATIENT SELECTION

3.1 Eligibility Criteria

- 3.1.1 Patients must have histologically or cytologically confirmed advanced or metastatic cancer for which capecitabine treatment is considered a standard treatment option.
- 3.1.2 Patients with **measurable or evaluable** disease are eligible
- 3.1.3 Patient's Body Mass Index must be 30 kg/m² or higher.
- 3.1.4 Eastern Cooperative Oncology Group performance status 0-2.
- 3.1.5 Age \geq 18 years.
- 3.1.6 Life expectancy of greater than 12 weeks.
- 3.1.7 Patients must have adequate organ and marrow function as defined below:
 Hematologic: ANC >1000/mcL, Hemoglobin > 8gm/dL (transfusions permitted) and platelets > 75,000/mcL

• Renal: serum creatinine \leq upper limit of normal (ULN) or creatinine clearance (either estimated or calculated) \geq 60 mL/min/1.73 m for patients with creatinine levels above institutional normal.

Females: $Cr_{cl} = (140\text{-}age)(weight in kg)(0.85)$ 72 x Serum creatinine

Males: $Cr_{cl} = (140\text{-age})(\text{weight in kg})$ 72 x Serum creatinine

- Hepatic: Serum Bilirubin ≤ 1.5 x ULN and
 - No liver metastases: AST and ALT \leq 2.5x ULN
 - Liver metastases: AST and $ALT \leq 5x ULN$

- 3.1.8 Ability to understand and the willingness to sign a written informed consent document.
- 3.1.9 Capecitabine is contra-indicated in pregnant women because of known detrimental effects on the fetus. A negative pregnancy test is required in all premenopausal women within 14 days of study therapy initiation. Women of child-bearing potential and men with an active female sexual partner must agree to use adequate contraception (hormonal, surgical, barrier methods or abstinence allowed) prior to study entry and for the duration of study participation. Should a woman become pregnant or suspect she is pregnant while participating in this study, she should inform her treating physician immediately.

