11. MEASUREMENT OF EFFECT

11.1 Antitumor Effect – Solid Tumors

For the purposes of this study, patients should be re-evaluated for response once at 6-9 weeks (+/- 1 week) after initiation of therapy, and then per discretion of treating physician.

Response and progression will be evaluated in this study using the new international criteria proposed by the Response Evaluation Criteria in Solid Tumors version 1.1 (RECIST) Committee [*JNCI* 92(3):205-216, 2000]. Changes in only the largest diameter (unidimensional measurement) of the tumor lesions are used in the RECIST 1.1 criteria.

11.1.1 **Definitions**

Evaluable for toxicity. All patients will be evaluable for toxicity from the time of their first treatment with capecitabine.

Evaluable for Pharmacokinetic Comparison: Patients will be evaluable for the primary endpoint if he or she takes 100% of their capecitabine dose days 1 through 9 and at least 90% of their capecitabine dose days 10 through 15 in cycle one.

Evaluable for objective response. Only those patients who have measurable disease present at baseline who have received at least one cycle of therapy (21)

days) will be considered evaluable for response. These patients will have their response classified according to the definitions stated below.

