11.1.2 Disease Parameters

Measurable disease. Measurable lesions are defined as those that can be accurately measured in at least one dimension (longest diameter to be recorded) as ≥ 20 mm with conventional techniques (CT, MRI, x-ray) or as ≥ 10 mm with spiral CT scan. All tumor measurements must be recorded in millimeters (or decimal fractions of centimeters).

Note: Tumor lesions that are situated in a previously irradiated area will not be considered measurable.

Non-measurable disease. All other lesions (or sites of disease), including small lesions (longest diameter <20 mm with conventional techniques or <10 mm using spiral CT scan), are considered non-measurable disease. Bone lesions, leptomeningeal disease, ascites, pleural/pericardial effusions, lymphangitis cutis/pulmonis, inflammatory breast disease, abdominal masses (not followed by CT or MRI), and cystic lesions are all non-measurable.

Target lesions. All measurable lesions up to a maximum of 5 lesions per organ and 10 lesions in total, representative of all involved organs, should be identified as **target lesions** and recorded and measured at baseline. Target lesions should be selected on the basis of their size (lesions with the longest diameter) and their suitability for accurate repeated measurements (either by imaging techniques or clinically). A sum of the longest diameter (LD) for all target lesions will be calculated and reported as the baseline sum LD. The baseline sum LD will be used as reference by which to characterize the objective tumor response.

Non-target lesions. All other lesions (or sites of disease) including any measurable lesions over and above the 10 target lesions should be identified as **non-target lesions** and should also be recorded at baseline. Measurements of these lesions are not required, but the presence or absence of each should be noted throughout follow-up.

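### Response category 9 in Section 13.5.2 gives measurable disease as the reason a patient cannot be assessed, which reverses Sections 11.1.1 and 11.1.4

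*Combined protocol and SAP*

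**What the plan says.** Response rate is a secondary objective (Section 1.2.1). Four parts of the protocol govern how it is coded and counted.

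- **Coding list, Section 13.5.2.** "Each patient will be assigned one of the following categories", and the last of these, category 9, is "unknown (not assessable due to measurable disease only or insufficient data").
- **Failure rule, same section.** "Patients in response categories 4-9 should be considered to have a treatment failure (disease progression").
- **Denominator, Section 13.4.** "All eligible subjects (intent-to-treat population) will be included in the calculation of the response rate".
- **Evaluability, Section 11.1.1.** "Only those patients who have measurable disease present at baseline", and who have had at least one 21-day cycle, are evaluable for objective response. Their response is then classified by the criteria that follow.

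Two definitions complete the picture. Section 11.1.2 states: "Measurable lesions are defined as those that can be accurately measured in at least one dimension". Section 3.1.2 admits patients with "measurable or evaluable" disease, so patients without any measurable lesion can enrol.

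**The concern.** Category 9 should collect patients whose response cannot be determined. Its wording instead names the disease status that makes response determinable under the rest of the protocol. Because categories 4 to 9 count as failure, and Section 13.4 keeps all eligible patients in the denominator, the category definition feeds directly into the response rate.

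Two groups are affected. Patients whose disease is entirely measurable meet a printed description that leads to failure. Patients whose disease is entirely non-measurable, for whom the category was presumably intended, have no clear code. At stake is whether the response rate in a small pilot is coded the same way by everyone who applies the list.

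**Working it through.** The plan states no figure on this point, so the check is a comparison of sections.

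**1. Can measurable disease be a reason for non-assessability?** Section 11.1.2 draws target lesions from measurable lesions. Section 11.1.4.1 defines partial response as a fall of at least 30% in the summed longest diameters of those target lesions. Section 11.1.1 requires measurable disease before response is classified at all. By all three, measurable disease is what makes assessment possible.

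**2. Test case A: measurable disease only.** Take a patient with two measurable liver lesions, a confirmed 40% shrinkage and no new lesions. Since 40% exceeds 30%, Section 11.1.4 gives partial response, category 2. The same patient also has the disease status that category 9 names as a cause of being unassessable. Section 13.5.2 requires one code and gives no order of precedence.

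**3. Test case B: non-measurable disease only.** Take a patient with bone lesions only, which Section 11.1.2 lists as non-measurable. There are no target lesions, so partial response is not defined, and Section 11.1.1 makes the patient non-evaluable. Category 9 does not mention this patient's situation. Only a generous reading of its insufficient-data clause would cover it.

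**4. Does another section correct the wording?** None does. Section 13.4 says response follows RECIST but points to Section 12, which covers data reporting. The criteria are in Section 11.

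**5. Can an effect be sized?** The response rate moves only when a complete or partial responder is recoded to 9. Let RR be the true rate, p the share of patients with measurable disease only, and q the chance that a responder among them is recoded. If response is equally likely in all patients:

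expected observed rate = RR × (1 − p × q)

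The documents give neither p nor q. Taking RR = 25.8%, the upper single-agent colorectal figure in Section 2.3:

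| p | q | Expected observed rate |
|---|---|---|
| any | 0 | 25.8% |
| 50% | 1 | 25.8% × 0.5 = 12.9% |
| 100% | 1 | 0% |

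The result runs from no effect to total loss, depending entirely on assumptions, so it is not an estimate of bias.

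**6. What remains after the wording is corrected?** Let N be the eligible patients, k those with non-measurable disease only (none of them counted as a responder) and r the responders. Sections 13.4 and 13.5.2 give r/N, with the k patients as category 9 failures. Section 11.1.1 drops them, giving r/(N − k) before its one-cycle condition is applied. The two differ whenever r and k are both above zero.

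**The case against.** The strongest reply is that nobody would code test case A as 9. The operative words of the category are unknown and not assessable; the reference to measurable disease only gives a cause. A confirmed partial response is neither unknown nor unassessable, and category 2 fits it directly. Section 13.4 determines response by RECIST, the table in Section 11.1.4.3 maps the patient to partial response, and Section 11.1.7 sends the imaging of every complete or partial responder for independent review. On this view the phrase is a one-word slip with no analytic consequence.

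Most of this stands as regards size. It does not rescue the text. The phrase still contradicts Section 11.1.1, the list has no precedence rule, and test case B still has no clear code even on the charitable reading.

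A reader might infer three stronger things that the documents do not support:

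- **A quantified downward bias in the response rate.** That needs an assumed p and the further assumption that every affected responder is recoded.
- **A 10-point drop per recoded responder.** That takes 10 as the denominator. Section 13.2 sets 10 for the pharmacokinetic comparison and replaces unevaluable patients, so the number of eligible patients may be larger.
- **False progression events in progression-free survival.** Section 11.1.6 defines that endpoint separately, by clinical or imaging evidence of progression.

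**Conclusion.** The category 9 wording is wrong as it stands. It reverses the evaluability rule in Section 11.1.1 and the target-lesion basis of Section 11.1.4, and it leaves patients with only non-measurable disease without a clear code. It should be corrected, because it sits in the operative rule for a stated secondary objective.

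Its practical weight is modest. A documented complete or partial response would probably still be coded 1 or 2, which is a judgement about how coders behave and is not stated in the protocol. The size of any bias cannot be derived from the documents. The plan sets no hypothesis test or decision threshold for response, and the primary AUC and Cmax comparison is untouched.

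The denominator conflict between Section 11.1.1 and Sections 13.4 and 13.5.2 should be settled together with the wording. Otherwise a corrected category 9 patient would be non-evaluable in one section and a failure in the other.

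**What to change.** 1. In Section 13.5.2, change measurable to non-measurable in the definition of category 9 and keep the insufficient-data clause.
2. Add a sentence saying that a patient with measurable disease and adequate scans is classified under Section 11.1.4 and is not coded 9 on account of having measurable disease. The early-death categories 5 to 7 must stay available; an instruction that such patients are always coded 1 to 4 would conflict with them.
3. State one primary denominator for the response rate, either all eligible patients or those evaluable under Section 11.1.1, and use it in Sections 11.1.1, 13.4 and 13.5.2. If both are wanted, label one as supportive.
4. While editing, correct the RECIST cross-reference in Section 13.4 so that it points to Section 11.

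The cost is a few lines of text. No new data, patients or procedures are needed.

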APPENDIX A

ECO	OG Performance Status Scale	Karnofsky Performance Scale		
Grade	Descriptions	Percent	Description	
0	Normal activity. Fully active, able	100	Normal, no complaints, no evidence of disease.	
0	performance without restriction.	90	Able to carry on normal activity; minor signs or symptoms of disease.	
1	Symptoms, but ambulatory. Restricted in physically strenuous activity, but ambulatory and able	80	Normal activity with effort; some signs or symptoms of disease.	
1	to carry out work of a light or sedentary nature (e.g., light housework, office work).	70	Cares for self, unable to carry on normal activity or to do active work.	
2	In bed <50% of the time. Ambulatory and capable of all self-care, but unable to carry out	60	Requires occasional assistance, but is able to care for most of his/her needs.	
	any work activities. Up and about more than 50% of waking hours.		Requires considerable assistance and frequent medical care.	
2	In bed >50% of the time. Capable of only limited self-care, confined	40	Disabled, requires special care and assistance.	
5	to bed or chair more than 50% of waking hours.	30	Severely disabled, hospitalization indicated. Death not imminent.	
1	100% bedridden. Completely disabled. Cannot carry on any	20	Very sick, hospitalization indicated. Death not imminent.	
4	self-care. Totally confined to bed or chair.	10	Moribund, fatal processes progressing rapidly.	
5	Dead.	0	Dead.	

Performance Status Criteria

APPENDIX B: Pill Diary

PATIENT'S MEDICATION DIARY - TEMPLATE

Today's dateAgent: CapecitabinePatient Name(initials acceptable)Patient Study ID

INSTRUCTIONS TO THE PATIENT: 1. Complete one form for each cycle of treatment. You will take _____ Capecitabine tablets twice daily. You should take the tablets in the morning 30 minutes after 2. eating and in the evening 30 minutes after eating at approximately same time each day. Record the date, the number of tablets of each size of tablet that you took, and when you took them. 3. If you have any comments or notice any side effects, please record them in the Comments column. 4. Please bring this form and your bottles of Capecitabine tablets when you return for each appointment. 5. Comments Time of AM Time of PM dose Dav Date dose 1 2 3 4 5 6 7 8 9 10 11 12 13 14 15 16 17 18 19 20 21

Patient's signature

Physician's Office will complete this section:

- 1. Date patient started protocol treatment
- 2. Date patient was removed from study_____
- 3. Patient's planned total daily dose _____
- 4. Total number of tablets taken this month _____
- 5. Physician/Nurse/Data Manager's Signature

APPENDIX C: UWinRx: The University of Wisconsin Policy for Standardizing Assessment of CYP Mediated Drug Interaction in Clinical Trials

Effective Date: October 1, 2011 Version: New Section: Phase I

I. Purpose

The purpose of this policy is to provide a framework for standardizing assessment of cytochrome p450 drug interactions with respect to clinical trial eligibility.

II. Definitions

- A. Investigational drug(s) is/are the drug(s) being evaluated in the clinical trial as determined by the study chair, lead investigator and Drug Interaction Task Force (DITF). In some cases these agents are commercially approved, but for the purpose of this policy they will be considered investigational.
- B. Concurrent medications are commercially available prescription and OTC being taken by the study subject but not mandated by the study protocol
- C. Pharmacokinetic Definitions
 - a. Inhibitors
 - i. *Strong inhibitor* is one that causes $a \ge 5$ -fold increase in the plasma AUC values or more than 80% decrease in clearance.
 - ii. *Moderate inhibitor* is one that causes $a \ge 2$ -fold, but <5-fold increase in the plasma AUC values or 50-79% decrease in clearance.
 - *Weak inhibitor* is one that causes a > 1.25-fold but < 2-fold increase in the plasma AUC values or 20-49% decrease in clearance.
 - b. Inducers are drugs which cause ≥30% change in plasma AUC values.
 Drugs with < 30% change are defined as noninducers. Lexi-comp defined major or moderate inducers are defined as inducers.
 - c. Substrates are categorized as sensitive or not sensitive.

- i. Sensitive refers to drugs whose plasma AUC values have been shown to increase 5-fold (CYP3A) or 2-fold (All other CYP) when co-administered with a known inhibitor.
- ii. Lexi-comp defined major substrates are sensitive, minor substrates are not sensitive.
- d. Narrow therapeutic index drugs are those where exposure-response indicates that increases in their exposure levels by the concomitant use of interacting medications may lead to serious toxicity
- D. Cmax is the maximum plasma concentration of the investigational agent
- E. Ki is the dissociation constant of enzyme inhibitor, which is needed to categorize an agents metabolic profile
- F. IC50 is the inhibitory concentration 50% and is not interchangeable with the Ki.
- G. Km, or the Michaelis–Menten concentration is when the rate of enzyme binding equals the rate of enzyme unbinding (steady state). If the IC50 determination was conducted at Km, the Ki=IC50/2
- H. In vitro Definitions
 - a. Inhibitors

Strong inhibitors: $Cmax/Ki \ge 1$ Moderate inhibitors: Cmax/Ki = 0.1-0.91Weak inhibitors: Cmax/Ki < 0.1

- b. Inducers: > 100% increase in enzyme activity
- c. Substrates

Sensitive: \geq 30% of metabolism occurs via a given CYP Not sensitive: < 30% of metabolism occurs via a given CYP

III. Policy

a. UWCCC clinical trials must include a section in the protocol or a "cheat sheet" in Oncore that defines the metabolic pathway (CYP enzyme and whether it is a substrate, (sensitive or not sensitive), inducer or inhibitor (strong, moderate or weak) of the investigational agent as well as the contraindicated concurrent medications.

- b. If there is no metabolic pathway section in the protocol, the study chair and/or lead investigator will prepare this section of the protocol or cheat sheet.
- c. The DITF, or subcommittee of the DITF, including one medical oncologist and one pharmacist, has responsibility for reviewing and approving the metabolic pathway section within 1 week.
- d. Patient concurrent medications,
 - i. Medications including route and schedule, for study candidates will be collected by Phase I nurses by patient interview
 - ii. List will be reviewed and categorized (CYP enzyme and whether it is a substrate, inducer and inhibitor) by PRC.
- e. Pharmacokinetic definitions from previous in vivo trials are the preferred method for categorizing interaction potential. In vitro data (Ki values) will be utilized if clinical definitions are not available.
- f. If only IC50 values are available, they should be converted to Ki values, as recommended by Cer et al, using the relationship Ki=IC50/2 with the assumption that the IC50 was conducted at the Km.
- g. The most recent version of the Drug Information Handbook (Lexi-Comp) will be used as the primary reference for assessment of interaction potential of concurrent medications. This reference is updated annually. The secondary references will be Micromedix and drug information leaflets (package inserts).
- h. The most recent version of the investigational drug brochure (IDB) will be used for assessment of interaction potential of the investigational agent.
- i. Transdermal products designed for systemic delivery must be assessed for interaction potential. Topical products not designed to provide systemic delivery, (including inhaled products, ophthalmologic products and transvaginal preparations) do not need to be considered since they do not have appreciable systemic absorption.
- j. All protocol mandated anti-cancer medications will be considered to be "narrow therapeutic index" drugs
- k. Concurrent medication that are "narrow therapeutic index" are defined as agents where a small change in plasma concentrations may result in substantial clinical impact, such as warfarin and drugs that affect the QT interval (Class I and III antiarrhythmics, antipsychotics, azoles, bepridil, dolasetron, fluoroquinolones,

fluoxetine, loratadine, macrolide antibiotics, methadone, ondansetron, phenothiazines, sulfamethoxazole, tolterodine, trazodone, tricyclic antidepressants, trimethoprim). Definition of narrow therapeutic index will be left to physician discretion

- IV. Procedure for Eligibility Determination
 - a. Phase I office will review medication regimens, including OTCs ; and email this medication profile to the PRC.
 - b. PRC will evaluate investigational agents and concurrent medications for interactions using table 1 or as stipulated in the protocol and categorize medications as Contraindicated, Use with Caution or Allowed.
 - i. PRC will determine the metabolic pathway of the investigational agent from the cheat sheet or protocol and locate on grey panel of table 1.
 - ii. PRC will determine the metabolic pathway of each concurrent medication from the most recent version of Lexi-Comp and locate on pink panel of table 1.
 - iii. PRC will determine the intersecting box.
 - c. Contraindicated medications must be discontinued for a patient to be eligible for the clinical trial. Since time frame for discontinuation will vary with type of interaction and drug half-life, this will be determined on a case by case basis by the study chair, PCR and/or DITF.
 - d. If patient is on one or more "Use with Caution" medications, the study chair and treating physician must be contacted for an eligibility determination.
 - e. Allowed medications are allowed without consultation with the study chair or treating physician

Investigationa			Concurrent	t Medicati	on	
l Agent	No CYP	Nonsensitiv	Sensitive	Weak	Strong and	Inducer
	Interactio	e Substrate	Substrate	Inhibitor	Moderate	
	n	but narrow			Inhibitor	
		therapeutic				
		index				
No CYP	Allowed	Allowed	Allowed	Allowed	Allowed	Allowed
Interaction						
Nonsensitive	Allowed	Allowed	Allowed	Allowed	Use with caution	Use with caution
Substrate						
Sensitive	Allowed	Allowed	Use with caution	Use	Contraindicated	Contraindicated
Substrate				with		
				caution		
Weak Inhibitor	Allowed	Allowed	Use with caution	Allowed	Use with caution	Use with caution
Strong and	Allowed	Use with**	Contraindicated*	Use	Use with	Contraindicated
Moderate#		caution		with	caution	
Inhibitor				caution		
Inducer	Allowed	Use with**	Contraindicated*	Use	Contraindicated	Contraindicated
		caution		with		
				caution		

Table 1: Matrix for Assessment of Interactions

*Contraindicated unless close monitoring with labs or drug levels and dose adjustment feasible

**Use with caution and consider monitoring with labs or drug levels and dose adjustment if feasible

If an investigational agents is categorized as a moderate inhibitor based on in vitro data only, follow recommendations for weak inhibitors

V. References

 $\underline{www.fda.gov/Drugs/DevelopmentApprovalProcess/DevelopmentResources/DrugInteractionsLabeling/ucm080499.htm}$

VI. Coordination

Phase 1 research office
